#### **9.4.4. Weight**

An additional key secondary endpoint is the percent change from baseline in weight at Week 24 and will be analyzed using an ANCOVA model, as described in Section 9.2.1. Subjects who are missing weight at Week 24 will have their data imputed through the multiple imputation procedure described in Section 16.2.

Statistical significance for the treatment comparison will be determined using the multiple comparison procedure described in Section 9.1. Descriptive statistics and LS means for percent change from baseline to Week 24 in weight will be presented by treatment group along with the LS-mean treatment difference, 95% confidence intervals, and p-value.

A tipping point sensitivity analysis of percent change from baseline in weight at Week 24 will be performed to assess the robustness of the missingness assumptions as was described for the

primary endpoint in Section 9.3.3. The implementation procedure for the tipping point analysis is described in Appendix 16.5 for each key secondary efficacy endpoint.

A complete-case sensitivity analysis will also be performed to test the robustness of the multiple imputation procedure. The ANCOVA analysis for percent change from baseline in weight will be repeated using only subjects with observed data at Week 24. Subjects who are missing the Week 24 secondary endpoint will be excluded from the analysis.

As a supplementary analysis, the absolute change from baseline in weight at Week 24 will be analyzed using the same method as described in the primary analysis of this endpoint. Missing data will also be imputed using the same methods as described in the primary analysis of this endpoint.

Descriptive statistics will be presented by treatment group and visit for weight observed, change from baseline, and percent change from baseline values. Mean ( $\pm$ SEM) observed values at each visit will be summarized in line graphs by treatment group. Similar graphs will be presented for the change from baseline and percent change from baseline values.

In the subset of subjects classified as overweight or obese ( $\text{BMI} \geq 25 \text{ kg/m}^2$  at baseline), the number and percentage of subjects achieving a greater than 5 percent reduction in total body weight from baseline to Week 24 will also be presented by treatment group.

In addition to weight, BMI observed and change from baseline values will be summarized with descriptive statistics by visit and treatment group. The change from baseline to Week 24 in BMI will be analyzed using an ANCOVA model, as described in Section 9.2.1. Missing data will be imputed using the same methods as described in the primary analysis of the change from baseline in weight (as described above). Descriptive statistics and LS means for the change from baseline to Week 24 in BMI will be presented by treatment group along with the LS-mean treatment difference, 95% confidence intervals, and p-value.

BMI will also be presented in the following categories: underweight ( $\text{BMI} < 18.5 \text{ kg/m}^2$ ), normal ( $\geq 18.5 \text{ to } < 25 \text{ kg/m}^2$ ), overweight ( $\geq 25 \text{ to } < 30 \text{ kg/m}^2$ ), obese I ( $\geq 30 \text{ to } < 35 \text{ kg/m}^2$ ), obese II ( $\geq 35 \text{ to } < 40 \text{ kg/m}^2$ ), obese III ( $\geq 40 \text{ kg/m}^2$ ). Descriptive statistics will be presented by treatment group for the number and percentage of subjects in each BMI category by visit.

Shifts from baseline to Week 24 in collapsed BMI categories will be presented in tables. The categories are defined as follows: underweight or normal ( $\text{BMI} < 25 \text{ kg/m}^2$ ), overweight ( $\geq 25 \text{ to } < 30 \text{ kg/m}^2$ ), and obese ( $\text{BMI} \geq 30 \text{ kg/m}^2$ ). Each shift table will have four rows and four columns, with rows reflecting the categories at baseline as well as missing values and columns reflecting the categories at Week 24 as well as missing values. A “Total” row and “Total” column will also be included. The number and percentage of subjects in each shift category will be displayed in the table; percentages will be based on the number of subjects included in the table.

#### **9.4.5. Total Fat Mass**

An additional key secondary endpoint is the change from baseline in percent total fat mass (calculated as total fat mass [g]/total body mass [g] \* 100) at Week 24 and will be analyzed using an ANCOVA model, as described in Section 9.2.1. Subjects who are missing percent total fat mass at Week 24 will have their data imputed through the multiple imputation procedure described in Section 16.2.

Statistical significance for the treatment comparison will be determined using the multiple comparison procedure described in Section 9.1. Descriptive statistics and LS means for change from baseline to Week 24 in percent total fat mass will be presented by treatment group along with the LS-mean treatment difference, 95% confidence intervals, and p-value.

Descriptive statistics will be presented by treatment group and visit for percent total fat mass observed and change from baseline values.

A tipping point sensitivity analysis of change from baseline in percent total fat mass at Week 24 will be performed to assess the robustness of the missingness assumptions as was described for the primary endpoint in Section 9.3.3. The implementation procedure for the tipping point analysis is described in Appendix 16.5 for each key secondary efficacy endpoint.

A complete-case sensitivity analysis will also be performed to test the robustness of the multiple imputation procedure. The ANCOVA analysis for change from baseline in percent total fat mass will be repeated using only subjects with observed data at Week 24. Subjects who are missing Week 24 percent total fat mass data will be excluded from the analysis.

As a supplementary analysis, the change from baseline in total fat mass (in kg) at Week 24 will be analyzed using the same method as described in the primary analysis of this endpoint. Missing data will also be imputed using the same methods as described in the primary analysis of this endpoint.

## **9.5. Analysis of Secondary Efficacy Endpoints**

The following sections describe the secondary efficacy endpoints and methods of summarization and analysis. For all analyses of the secondary efficacy endpoints, missing data will not be imputed and only observed cases will be used. All p-values produced from the analyses in this section will be considered nominal p-values and will not be adjusted for multiplicity.

### **9.5.1. 17-OHP**

Change from baseline to Week 4 in 17-OHP is a secondary endpoint. The pre-morning glucocorticoid dose 17-OHP values at baseline and Week 4 will be used in the calculation of this endpoint (as described in Section 6.3.5). If a subject is missing their Week 4 pre-glucocorticoid dose 17-OHP value, then the post-glucocorticoid 17-OHP values at baseline and Week 4 will be used instead.

The analysis of this endpoint will be performed using an analysis of covariance (ANCOVA) model, as described in Section 9.2.1. Descriptive statistics and LS means for change from baseline to Week 4 in 17-OHP will be presented by treatment group along with the LS-mean treatment difference, 95% confidence intervals, and p-value.

Descriptive statistics will be presented by treatment group and visit for 17-OHP observed and change from baseline values. Mean ( $\pm$ SEM) values of 17-OHP at each visit will be summarized in line graphs by treatment group. For visits where 17-OHP is collected more than once (e.g., Day 1), each timepoint will be presented with the pre- and post- morning GC dose 17-OHP values on separate plots. Similar graphs will be presented for the changes from baseline.

As a supplementary analysis, the percent change from baseline in 17-OHP will be analyzed using the same method as described in the primary analysis of this endpoint.

As a supplementary analysis, the change from baseline to Week 4 in 17-OHP, derived as a multiple of the ULN (based on age and sex), will be analyzed using the same method as described in the primary analysis of this endpoint.

### **9.5.2. Blood Pressure**

Change from baseline to Week 24 in blood pressure is a secondary endpoint. For the purpose of analysis and summarization, the average of the triplicate sitting blood pressure values at each visit will be used. Systolic blood pressure (SBP), diastolic blood pressure (DBP), and mean arterial pressure (MAP; calculated as  $MAP = DBP + 1/3[SBP - DBP]$ ) will be analyzed using an ANCOVA model (as described in Section 9.2.1). Descriptive statistics and LS means for change from baseline to Week 24 in SBP, DBP, and MAP will be presented by treatment group along with the LS-mean treatment differences, 95% confidence intervals, and p-values.

Descriptive statistics will be presented by treatment group and visit for SBP, DBP, and MAP observed and change from baseline values.

### **9.5.3. Glucose Tolerance**

Change from baseline to Week 24 in glucose tolerance (in subjects without diabetes mellitus) is a secondary endpoint. Subjects with a medical history of diabetes mellitus or who meet criteria for diabetes mellitus based on the Day 1 glucose tolerance test (fasting glucose  $\geq 126$  mg/dL [6.993 mmol/L] or post-glucose load  $\geq 200$  mg/dL [11.1 mmol/L]) or HbA1c (HbA1c  $\geq 6.5\%$ ) will be excluded from this analysis. The analysis of this endpoint will be based on the post-GTT glucose values and performed using an ANCOVA model, as described in Section 9.2.1. Descriptive statistics and LS means for change from baseline to Week 24 in glucose tolerance will be presented by treatment group along with the LS-mean treatment difference, 95% confidence intervals, and p-value.

The change in glucose values from pre-glucose load to post-glucose load will also be calculated by subject for the baseline and Week 24 visits. Descriptive statistics for the observed and change from baseline glucose values for the pre-glucose load, post-glucose load, and differences between the pre- and post-glucose loads will be summarized by treatment group.

Shifts from baseline to Week 24 in the post-GTT glucose level categories will be presented in tables. The categories are defined as follows: post-GTT glucose levels  $< 140$  mg/dL (7.77 mmol/L) (normal blood glucose level), post-GTT glucose levels  $\geq 140$  mg/dL (7.77 mmol/L) and  $< 200$  mg/dL (11.1 mmol/L) (impaired glucose tolerance/prediabetes), or post-GTT glucose levels  $\geq 200$  mg/dL (11.1 mmol/L) (diabetes mellitus). Each shift table will have four rows and four columns, with rows reflecting the categories at baseline as well as missing values and columns reflecting the categories at Week 24 as well as missing values. A “Total” row and “Total” column will also be included. The number and percentage of subjects in each shift category will be displayed in the table; percentages will be based on the number of subjects included in the table.

Shifts from baseline to Week 24 in pre-GTT glucose level categories will also be presented in tables. The categories are defined as follows: pre-GTT fasting glucose levels  $< 100$  mg/dL (5.55 mmol/L) (normal fasting blood glucose level), pre-GTT glucose levels  $\geq 100$  mg/dL (5.55

mmol/L) and < 126 mg/dL (6.993 mmol/L) (impaired fasting glucose/prediabetes), or pre-GTT glucose levels  $\geq$  126 mg/dL (6.993 mmol/L) (diabetes mellitus). Each shift table will have four rows and four columns, with rows reflecting the categories at baseline as well as missing values and columns reflecting the categories at Week 24 as well as missing values. A “Total” row and “Total” column will also be included. The number and percentage of subjects in each shift category will be displayed in the table; percentages will be based on the number of subjects included in the table.

#### **9.5.4. Waist Circumference**

Change from baseline to Week 24 in waist circumference (in centimeters) is a secondary endpoint. The analysis of this endpoint will be performed using an ANCOVA model, as described in Section 9.2.1. Descriptive statistics and LS means for change from baseline to Week 24 in waist circumference will be presented by treatment group along with the LS-mean treatment difference, 95% confidence intervals, and p-value.

Descriptive statistics will be presented by treatment group and visit for waist circumference observed and change from baseline values.

#### **9.5.5. Menstrual Regularity**

Menstrual regularity at Week 24 (in female subjects of childbearing potential who are not on hormonal or intrauterine device contraceptives) is a secondary endpoint. Subjects meeting these criteria were asked to input the dates for which they were assessing their menstrual cycle as well as the amount of flow (light [spotting], medium [normal flow], heavy [heavy flow with flooding or clotting]). For the purposes of this analysis, a menstrual cycle will be defined as two consecutive calendar days with any amount of flow. Menstrual cycle regularity is defined as a menstrual cycle every 21-35 days, translating to approximately 4 to 8 menstrual cycles from baseline to Week 24. The number and percentage of subjects meeting the definition for regular menstrual cycle at Week 24 will be summarized by treatment group. This summary will be stratified based on menstrual cycle regularity at study entry (as collected on the CAH medical history eCRF, “Do menstrual cycles typically occur every 21-35 days?”). This endpoint will be analyzed using a CMH test as described in Section 9.2.2. The CMH test will compare treatment groups and will include the stratification factors used in the randomization (with the exception of sex) as well as menstrual cycle regularity at study entry. The p-value from the CMH analysis will also be displayed in a table.

#### **9.5.6. Testicular Adrenal Rest Tumors (TARTs)**

For male subjects with TARTs, the length, width, and depth of each lesion will be measured and recorded on the eCRF. Both local and central readings were performed for the ultrasound data. Only data from the central reading will be analyzed. For the purpose of summarization and analysis, the volume of each lesion will be used to assess size (in cubic millimeters) at visits where the testicular ultrasound is performed. Volume will be calculated using the following formula: volume = length x width x depth x 0.5236. The volume of each testicle will be calculated using the same formula. Descriptive statistics will be used to summarize the total TART volume (calculated as the sum of the volume of each lesion across both testes) for each subject by treatment group and visit. Observed and change from baseline values will be included in the summary table.

Additionally, the total TART volume will be expressed as a percentage of the total testicular volume and calculated as the sum of the volume of each lesion across both testes divided by the total testicular volume across both testes for each subject. The total TART volume as a percentage of the total testicular volume will be summarized with descriptive statistics by treatment group and visit. Observed and change from baseline values will be included in the summary table.

Change from baseline to Week 24 in total TART volume as a percentage of total testicular volume is a secondary endpoint. The analysis of this endpoint will be performed in all male subjects (regardless of TART status at baseline) using an ANCOVA model, as described in Section 9.2.1 (with the exception of sex as a stratification factor in the model). Descriptive statistics and LS means for change from baseline to Week 24 in total TART volume as a percentage of total testicular volume will be presented by treatment group along with the LS-mean treatment difference, 95% confidence intervals, and p-value.

The number and percentage of subjects with the presence of TARTs (Y/N), whether they are unilateral or bilateral, and the average number of TARTS per subject will be summarized with descriptive statistics by visit and treatment group. The number and percentage of TARTs with each shape (round; lobular; irregular), boundary (clear; indistinct), hypervascularity (Y/N), calcification (Y/N), and the echogenicity will be summarized with descriptive statistics by visit and treatment group.

A response assessment will be conducted at Week 24 for subjects with the presence of TARTs at baseline. Response categories and the criteria for each category are detailed in Table 9. The frequency and percentage of subjects meeting each classification at Week 24 (as compared to baseline) will be summarized by treatment group. Complete responder will be analyzed using a CMH test as described in Section 9.2.2. Complete or partial responders (pooled together) will also be analyzed using a CMH test as described in Section 9.2.2. The CMH test will compare treatment groups and will include the stratification factors used in the randomization (with the exception of sex). The p-value from the CMH analysis will also be displayed in a table.

**Table 9: Response Categories**

Response Category	Definition
Complete Response (CR)	Disappearance of all TARTs.
Partial Response (PR)	$\geq 30\%$ decrease in total TART volume compared with baseline
Progressive Disease (PD)	$\geq 30\%$ increase in total TART volume compared with baseline
Stable Disease (SD)	Neither CR, PR nor PD

## **9.6. Exploratory Efficacy Endpoints**

The following sections describe the exploratory efficacy endpoints and methods of summarization and analysis. For all analyses of the exploratory efficacy endpoints, missing data

will not be imputed and only observed cases will be used. All p-values produced from the analyses in this section will be considered nominal p-values and will not be adjusted for multiplicity.

### **9.6.1. Hormone Measurements**

ACTH, total testosterone, follicle stimulating hormone (FSH), luteinizing hormone (LH), sex hormone binding globulin (SHBG), and progesterone will be summarized with descriptive statistics by visit and treatment group. Note that for hormone parameters that were collected both pre- and post-GC dose, the following summaries will be produced for both pre-GC dose and post-GC dose values. Both observed and change from baseline values will be displayed. All summaries of testosterone and progesterone will be stratified by sex. Summaries of FSH, LH, and SHBG will also be stratified by sex as well as by combined sexes. The change from baseline to Week 24 for each of these parameters will be analyzed using an ANCOVA model as described in Section 9.2.1. Descriptive statistics and LS means for change from baseline to Week 24 in each of these hormone parameters will be presented by treatment group along with the LS-mean treatment difference, 95% confidence intervals, and p-value.

Shifts from baseline to Week 4 in gonadotropin values (LH and FSH) will be presented in tables by sex as well as by combined sexes. Postmenopausal women will be excluded from the shift tables. Each shift table will have four rows and four columns, with rows reflecting the reference range category at baseline (low, normal, high, missing), and columns reflecting the reference range category at Week 4 (low, normal, high, missing). A “Total” row and “Total” column will also be included. The number and percentage of subjects in each shift category will be displayed in the table; percentages will be based on the number of subjects included in the table.

The achievement of response at Week 24 (as defined for each of the following responder analyses described below) will be analyzed using a CMH test as described in Section 9.2.2. The CMH test will compare treatment groups and will include stratification factors (with the exception of sex) used in the randomization. Subjects who are missing Week 24 data will be omitted from the analysis.

A responder definition for the normalization of LH will be defined as subjects with abnormal LH levels at baseline (defined as < LLN or > ULN) and achieve normalization at Week 24 in male subjects (based on pre-GC dose LH levels). The number and percentage of subjects meeting this responder definition at Week 24 will be summarized by treatment group. This responder definition and summarization will also be repeated for FSH.

A responder definition for the normalization of testosterone in female subjects will be defined as female subjects with testosterone levels that are greater than or equal to 1.2x ULN (based on age) at baseline and decrease to within the normal range at Week 24 based on the average of the pre-glucocorticoid and post-glucocorticoid testosterone levels at the applicable visit. The number and percentage of female subjects meeting this responder definition at Week 24 will be summarized by treatment group.

A responder definition for the normalization of progesterone in female subjects of child-bearing potential not on hormonal contraceptives will be defined as female subjects with a progesterone level >0.6 ng/mL at baseline and decrease to a progesterone level <0.6 ng/mL at any point during the DB period of the study. The average of the progesterone levels will be used at visits where more than one hormone sample is collected. This analysis will be restricted to female subjects

who are of childbearing potential and are not on hormonal contraceptives. The number and percentage of female subjects in this subset meeting this responder definition at each visit in the DB period will be summarized by treatment group.

A responder definition for the ratio of androstenedione to testosterone (A4/T) in male subjects will be defined as male subjects who have A4/T greater than or equal to 0.5 (based on the pre-glucocorticoid dose values for androstenedione and testosterone) at baseline and who achieve A4/T less than 0.5 at Week 24. The number and percentage of male subjects meeting this responder definition at Week 24 will be summarized by treatment group.

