**Table 3: Hormone Reference Ranges**

Hormone Reference Ranges	
Lab Analyte	Reference Ranges: conventional units; SI units
Androstenedione (conversion factor from ng/dL to nmol/L: x 0.0349)	
Adult Male:
 
18-30 years: 50-220 ng/dL; 1.745 - 7.678 nmol/L
 
31-50 years: 40-190 ng/dL; 1.396 - 6.631 nmol/L
 
51-60 years: 50-220 ng/dL; 1.745 - 7.678 nmol/L
 
Adult Female:
 
Mid Follicular: 51-213 ng/dL; 1.7799 - 7.4337 nmol/L
 
Surge: 73-230 ng/dL; 2.5477 - 8.027 nmol/L
 
Mid Luteal: 73-184 ng/dL; 2.5477 - 6.4216 nmol/L
 
Postmenopausal: 20-75 ng/dL; 0.698 - 2.6175 nmol/L

17-OH Progesterone (17-OHP) (conversion factor from ng/dL to nmol/L: x 0.0303)	
Adult Male:
 
18-30 years: 32-307 ng/dL; 0.9696 - 9.3021 nmol/L
 
31-40 years: 42-196 ng/dL; 1.2726- 5.9388 nmol/L
 
41-50 years: 33-195 ng/dL; 0.9999 - 5.9085 nmol/L
 
51-60 years: 37-129 ng/dL; 1.1211 - 3.9087 nmol/L
 
>= 61 years: Not established
 
Adult Females:
 
Pre-menopausal mid follicular: 23-102 ng/dL; 0.6969 - 3.0906 nmol/L
 
Pre-menopausal surge: 67-349 ng/dL; 2.0301-10.5747 nmol/L
 
Pre-menopausal mid luteal: 139-431 ng/dL; 4.2117 - 13.0593 nmol/L
 
Post-menopausal phase: <=45 ng/dL; 1.3635 nmol/L

Progesterone (conversion factor from ng/mL to nmol/L: x 3.18)	Male: <0.15ng/mL; 0.477 nmol/L, <0.48 nmol/L; 1.5264 nmol/L  Female: Premenopausal, not pregnant: <23.90 ng/mL, <76 nmol/L Female, pregnant: 11.00 – 214 ng/mL, 34.98 - 680.52 nmol/L Female, postmenopausal: <0.13 ng/mL, <0.41 nmol/L
ACTH (conversion factor from pg/mL to pmol/L: x 0.22)	Males and Females: 7.2 – 63.3 pg/mL; 1.584 -13.926 pmol/L
Follicle stimulating hormone (FSH) (conversion factor from mIU/mL to IU/L: x 1.0)	Male: 1.6 - 11.0 mIU/mL (IU/L) Female: 1.8 - 20.4 mIU/mL (IU/L)
Luteinizing Hormone (LH) (conversion factor from mIU/mL to IU/L: x 1.0)	Male: 1.7 - 8.6 mIU/mL (IU/L) Female: 1.0 - 95.6 mIU/mL (IU/L)
Sex Hormone Binding Globulin (SHBG)	Male: 10.0 - 80.0 nmol/L (same in SI) Female: 20.0 - 130.0 nmol/L (same in SI)
Total Testosterone (Medpace/MRL) (conversion factor from ng/mL to nmol/L: x 3.47)	Male: 2.70- 10.70 ng/mL; 9.37-37.13 nmol/L Female: 0.06 - 0.86 ng/mL; 0.21-2.98 nmol/L
Total Testosterone (Quest) (conversion factor from ng/dL to nmol/L: x 0.0347)	Male: 250 - 1100 ng/dL; 8.675 - 38.17 nmol/L Female: 2 - 45 ng/dL; .0694 - 1.5615 nmol/L

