**Figure 1: Procedure to Control for Multiple Comparisons**

## 9.2. Statistical Models

### 9.2.1. ANCOVA - continuous endpoints

The continuous efficacy endpoints will be analyzed using an analysis of covariance (ANCOVA) model, which includes the change (or percent change) from baseline to the respective postbaseline visit where the endpoint is being evaluated. The model will include the relevant baseline value as a covariate, treatment group (crinecterfont 100 mg bid; placebo), and stratification factors used in the randomization. Values of the stratification factors entered during randomization in IRT will be used in the primary analysis methods. Any corrected values as reported in the eCRFs for the stratification factors may be used in any supplementary or exploratory analyses and will be stated as such.

An example of the SAS software code is provided below. Note that the PROC MIXED statements shown in this section will be accompanied by additional statements to create and output the required statistics.

```
PROC MIXED;  
CLASS SEX GC_TYPE GC_DOSE TRTP;  
MODEL CHG = TRTP BASE SEX GC_TYPE GC_DOSE;  
RUN;
```

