### **9.7. Examination of Subgroups**

The following subgroups have been pre-planned and will be used to examine consistency of effect for the primary efficacy endpoint:

- Region (OUS versus US)
- Glucocorticoid type – dexamethasone use (subjects on dexamethasone at baseline versus subjects not on dexamethasone at baseline)
- Glucocorticoid type – hydrocortisone vs. synthetic glucocorticoids (subjects on hydrocortisone alone versus subjects on prednisone [or equivalent] or dexamethasone)
- Sex (male versus female; based on the eCRF)
- BMI ( $< 30 \text{ kg/m}^2$  vs.  $\geq 30 \text{ kg/m}^2$ )
- Race
- Ethnicity
- Age ( $< 65$  years vs.  $\geq 65$  years)
- Baseline total daily glucocorticoid dose ( $<20 \text{ mg/m}^2/\text{day}$  versus  $\geq 20 \text{ mg/m}^2/\text{day}$ ; based on the eCRF)

If any of these categories are sparse in number of subjects (e.g.,  $<15$ ), the categories with the fewest number of subjects may be collapsed until there are at least 15 subjects or the subgroup analysis may be omitted entirely. The decision to omit a subgroup analysis will be justified in the CSR. Each subgroup will be analyzed separately using an ANCOVA model that is similar to the model used in the primary analysis of the primary endpoint (as described in Section 9.2.1), with the addition of the subgroup variable added as a main effect term and an interaction term between treatment group and the subgroup variable. Note that for the sex, baseline glucocorticoid type, and baseline total daily glucocorticoid dose ( $<20 \text{ mg/m}^2/\text{day}$  versus  $\geq 20 \text{ mg/m}^2/\text{day}$ ), the values reported on the eCRF will be used in the model instead of the values reported as stratification factors in the IRT. Nominal two-sided p-values for comparing treatment groups and the associated 95% confidence intervals will be reported in summary tables and a forest plot, with p-values for the interaction term between treatment groups and subgroup variables will be presented.

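### The Week 24 hormone ANCOVA in SAP 9.6.1, read literally, pools men and women under one treatment effect, so for testosterone in particular an effect in one sex can be masked by the other

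*SAP*

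**What the plan says.** SAP 9.6.1 first describes descriptive summaries of ACTH, testosterone, FSH, LH, SHBG and progesterone. On layout it says "All summaries of testosterone and progesterone will be stratified by sex", and then "Summaries of FSH, LH, and SHBG will also be stratified by sex as well as by combined sexes". The inferential sentence follows with no mention of sex: "The change from baseline to Week 24 for each of these parameters will be analyzed using an ANCOVA model as described in Section 9.2.1". LS means, a treatment difference, 95% confidence intervals and a p-value are planned for each hormone.

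The code in SAP 9.2.1 is "MODEL CHG = TRTP BASE SEX GC_TYPE GC_DOSE". It has one treatment coefficient, one baseline slope and sex as an additive term, with no interaction and no separate fit by sex.

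Elsewhere the SAP states when sex leaves the model. For TARTs (9.5.6) the ANCOVA is run "with the exception of sex as a stratification factor in the model", and hirsutism (9.6.6) and acne (9.6.7) carry a similar exception. For the responder tests within 9.6.1 it says "The CMH test will compare treatment groups and will include stratification factors (with the exception of sex) used in the randomization". Treatment-by-subgroup interactions are confined to the primary endpoint (9.7): "The following subgroups have been pre-planned and will be used to examine consistency of effect for the primary efficacy endpoint".

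**The concern.** Levels of these hormones differ by sex, and the SAP expects changes of interest to differ too: its responder definitions look for testosterone and progesterone normalization in women, and for LH, FSH and A4/T changes in men. A single treatment coefficient averages the two sexes, and its standard error is driven by whichever sex varies more. If the effects differ, the planned LS-mean difference and p-value describe neither sex. A pooled null for testosterone could then be reported beside a positive responder result in women.

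**Working it through.** **Plan's own figure.** The documents give no power for the hormone ANCOVAs. As a check on method, the primary-endpoint power (Protocol 13.4, SAP 3.3) reproduces by two-sample t-test at two-sided 0.05: effect size 0.75 with 60/30 gives 91.3%, and 0.55 with 110/55 gives 91.2%. Both agree with the stated figure of more than 90%.

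**Formulas.** Let f be the share of women, dF and dM the true effects, and sF and sM the residual SDs.

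- Pooled estimate = f·dF + (1−f)·dM
- Pooled SD = √[f·sF² + (1−f)·sM²]
- Pooled SE = SD × √(1/55 + 1/110) = SD × 0.1651
- Women only at f = 0.5 (55 active, 27.5 placebo): SE = sF × √(1/27.5 + 1/55) = sF × 0.2335
- Power = Φ(|z| − 1.96) + Φ(−|z| − 1.96), where z = estimate/SE

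N = 165 and 2:1 allocation are from the documents. They give no SD of change and no sex split, so those are assumed.

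**Testosterone, assumed values in ng/dL.** Women −20 (SD 30), men 0 (SD 120 to 150), half women. The pooled estimate is −10.

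- Male SD 120: SD = √(450 + 7,200) = 87.5; SE = 14.44; |z| = 0.69; power 10.6%.
- Male SD 150: SD = √(450 + 11,250) = 108.2; SE = 17.86; |z| = 0.56; power 8.7%.
- Women only: SE = 7.01; |z| = 2.85; power 81%. Simulation gave 79% to 80%.

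**All five hormones.** Here the width of the Table 3 range stands in for the SD, with half women. For example, testosterone on the first assay is "Male: 2.70- 10.70 ng/mL; 9.37-37.13 nmol/L" against 0.06 to 0.86 ng/mL in women, so the widths are 8.00 and 0.80. For progesterone the upper limits are used (0.15 ng/mL in men, 23.90 in premenopausal women). The effect is 0.75 SD of the affected sex, with none in the other. A one-sex fit then has 89.5% power throughout.

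| Hormone | Width, men / women | Male share of pooled variance | Pooled power, effect in women only | Pooled power, effect in men only |
|---|---|---|---|---|
| Testosterone, first assay | 10.0 | 99.0% | 6.2% | 89.2% |
| Testosterone, second assay | 19.8 | 99.7% | 5.3% | 89.4% |
| SHBG | 0.64 | 28.8% | 77.3% | 40.7% |
| FSH | 0.51 | 20.3% | 81.8% | 30.5% |
| LH | 0.07 | 0.5% | 89.3% | 5.6% |
| Progesterone | 0.006 | about 0% | 89.5% | 5.0% |

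Simulation of the pooled model with treatment, baseline and sex (3,000 runs) agrees for an effect in women: testosterone 6.6% against 88.4% in women only, FSH 80.6% against 89.2%, SHBG 74.3% against 88.1%. With 40% to 60% women, pooled testosterone power is 5.2% to 7.1% and women-only power 81.9% to 94.0%.

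**Offsetting.** With dM = −dF the pooled estimate is (2f − 1)·dF: zero at half women, and ±0.2·dF at 60% or 40%.

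**The case against.** The best defence is that the sentences just before the ANCOVA stratify the summaries by sex, so separate fits may be intended. Most of the SAP's explicit exclusions of sex concern endpoints measured in one sex only, and say little about how it would word a model run in each sex in turn. This makes a by-sex reading possible, but the text does not state it. A by-sex fit cannot use the 9.2.1 model unmodified, because sex would be constant. It is also unclear whether the p-values for FSH, LH and SHBG would come from by-sex or combined fits.

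The second defence is mitigation, and it stands. The by-sex tables of observed values and changes would show a fall in women, and one-sex responder tests are planned.

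Two stronger readings are tempting. A reader might infer that male variance swamps an effect in women for all five hormones. Table 3 contradicts this: the range is wider in women for progesterone, LH, FSH and SHBG. A reader might also infer that the pooled result would carry the wrong sign for women. Arithmetically, −20 in women and +50 in men gives 0.5 × (−20) + 0.5 × 50 = +15 ng/dL. But nothing in the documents predicts a rise in men. The A4/T responder does not imply one, since that ratio can fall through lower androstenedione alone.

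**Conclusion.** The concern holds as an unclear and, on its literal wording, pooled specification. It bites hardest for testosterone, where an effect in women that a women-only model would detect about 80% of the time is detected about 9% to 11% of the time. Progesterone and LH have the mirror-image problem for an effect in men. For FSH and SHBG the loss is smaller for an effect in women and larger for one in men.

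The sizes rest on assumed SDs, effects and sex split. Range widths are only a rough proxy: CAH patients may differ from the reference population, the female LH and progesterone ranges span cycle phases, and the postmenopausal progesterone limit is far lower (0.13 ng/mL). The direction for testosterone is secure given a 10- to 20-fold difference in width.

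The stakes are low. SAP 9.6 makes these p-values nominal and unadjusted, and no primary or key secondary conclusion depends on them. The documents do not support saying that a real change in women would go unseen.

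**What to change.** Add to SAP 9.6.1: *The ANCOVA for testosterone and progesterone will be fitted separately in male and female subjects, with sex removed from the model; for FSH, LH and SHBG it will be fitted separately by sex, with the combined-sex model presented alongside.* This matches the display already chosen for the summaries and keeps combined-sex inference where the SAP wants it.

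No new data are needed. The cost is roughly half the sample in each fit if the sexes are balanced, and more nominal p-values, multiplied again where both pre- and post-glucocorticoid values are analyzed.
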